1.25 Missing Data and Dropouts

For all endpoints, the primary analysis will be intention-to-treat (ITT): all subjects randomized with a post-intervention endpoint measurement will be included. For endpoints based on measurements collected at the end of the study, individuals who do not complete follow-up cannot be included in analyses of those endpoints. Subjects who stop study interventions at any point of the study but agree to come back for the final data collection will be invited to do so to facilitate the ITT analysis. A per-protocol analysis will be conducted as a secondary analysis for the primary endpoints. Any subject who is identified as a major protocol violator will not be included. Major protocol violators will be defined as subjects randomized but non-compliant with wearing the accelerometer (i.e. missing $\geq 1/2$ of total days) and others

identified by a committee not related to the study (XXX usually the study team determines a list of protocol violators before data un-blinding, but this is a single blinded study and that [name] and [name] know who gets what and the endpoints, that complicates it a bit) .

Subjects who drop out will be replaced up to a total of 35 per group. Built-in alerts will be triggered if there is a prolonged lapse in data transmission in real-time activity tracking. Protocols to email, then call subjects will be followed to determine the cause of missing data and find a solution. The Fitbit device will store data for 28 days so even if data is not being transmitted, it will not be lost. A stock of new devices will be kept on hand to overnight ship to subjects if the Fitbit device fails to capture data or stops working.

In the event of missing data, we will conservatively impute missing data to perform analyses with and without imputed missing data to corroborate findings.

Conservative imputation strategies could include assuming worst case scenario for subjects on the intervention, best case for subjects on the control, or assuming the observed mean of the control group for the subjects on the intervention. A multiple imputation procedure implemented in the aregImpute function in the Hmisc package in R (R Package; Version 3.0-10) will be used. The analysis with imputation will serve primarily as a sensitivity analysis. The potential drop-out is considered in the power calculation to minimize its impact.

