1.24 Statistical Analysis

The primary analyses will focus on metformin vs placebo, exercise vs placebo, and metformin + exercise vs placebo comparisons on the primary endpoint. Since the evaluation of metformin or exercise will be reported as if they were independent studies and the combination arm versus placebo comparison serves to corroborate findings of the two separate comparisons, in addition to evaluating an additive or synergistic effect, we will not adjust for multiple comparisons. For binary endpoints, the Pearson chi-square or Fischer's exact test will be used to assess between treatment arms difference. Logistic regressions will be conducted to examine the treatment effect while adjusting for important covariates such as baseline 6MWD, functional status, age, and study site. Model over-fitting will be avoided by considering the number of parameters in the model and the number of responders in the sample. Continuous endpoints will be analyzed using either two-sample t-test or ANOVA, or non-parametric methods Wilcoxon Rank Sum test or Kruskal-Wallis test. Multivariable regressions (general linear models) will be conducted to examine the treatment effect while adjusting for important covariates such as baseline 6MWD, functional status, age, and study site. We have designed the study to minimize the potential for missing data. Subjects who drop out will be replaced up to a total of 35 per group. Nevertheless, in the event we have missing data, a multiple-imputation procedure as implemented in the aregImpute function in the Hmisc package in R (R Package; Version 3.0-10) will be used to assess the impact of missing data. The analyses with imputation will mainly serve as sensitivity analyses.

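### The primary analysis in section 1.25 is called intention-to-treat but keeps only subjects measured at week 12, so deaths and failing patients who miss that visit leave the denominator of a yes/no endpoint

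*Combined protocol and SAP*

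**What the plan says.** Section 1.25 (Missing Data and Dropouts) names the primary analysis for all endpoints intention-to-treat, then limits the set: "all subjects randomized with a post-intervention endpoint measurement will be included". For endpoints measured at the end of the study it adds that "individuals who do not complete follow-up cannot be included in analyses of those endpoints".

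Section 1.21.1 defines a responder by a gain of at least 10% in six-minute walk distance, or by at least one functional class, at week 12. Sections 1.22.2 and 1.22.5 schedule both measurements at screening and week 12 only. No section says how death or a missed week-12 visit counts towards response; death and hospitalisation for PAH are separate secondary outcomes.

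The plan also contains real mitigation:

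- A two-week run-in intended partly to limit later dropout (section 1.15).
- Return of subjects who stop treatment: "Subjects who stop study interventions at any point of the study but agree to come back for the final data collection will be invited". Section 1.48 asks for scheduled assessments to continue after withdrawal from treatment.
- CONSORT reporting of the numbers completing week 12 (section 1.23).
- A commitment on imputation: "we will conservatively impute missing data to perform analyses with and without imputed missing data to corroborate findings". The conservative rule is left open: "Conservative imputation strategies could include assuming worst case scenario for subjects on the intervention, best case for subjects on the control", with a control-group mean as a further option. "A multiple imputation procedure implemented in the aregImpute function" is also named.

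The role of these analyses is stated twice: "The analysis with imputation will serve primarily as a sensitivity analysis" (section 1.25) and "The analyses with imputation will mainly serve as sensitivity analyses" (section 1.24).

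The Protocol Summary and sections 1.24 and 1.25 allow dropouts to be replaced up to 35 per group, without saying whether the replaced subjects stay in the analysis.

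**The concern.** With no post-baseline value of either component before week 12, having a post-intervention measurement means having attended week 12. The set is therefore a completer set under an intention-to-treat label.

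For a continuous walk distance it is fair to say that a subject without a week-12 test supplies no value. For a yes/no response it is not: a subject who has died has plainly not responded, and one who deteriorated and did not return can be classed the same way.

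The headline response rate in each arm then depends partly on who attends. If one arm loses more failing patients than the other, its rate rises relative to the other with no treatment effect. Sections 1.24 and 1.25 do not say which result prevails if the completer and imputed analyses disagree.

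**Working it through.** **Inputs.** Section 1.26: 73% response on active treatment and 40% on placebo, 35 completed and 40 enrolled per group, type I error 0.05, 80% power, dropout under 10%. Section 1.24: Pearson chi-square or Fisher's exact test. The documents give no split of loss by arm or by reason, so every loss pattern below is an assumption.

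**1. The plan's own figure.** The active rate is 0.40 + 0.50 − 0.17 = 0.73. With pooled variance and a two-sided test, the mean rate is 0.565 and

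n = [1.96 √(2 × 0.565 × 0.435) + 0.842 √(0.73 × 0.27 + 0.40 × 0.60)]² / 0.33² = (1.374 + 0.556)² / 0.1089 ≈ 34.2, rounded up to 35.

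Normal-approximation power at 35 is 80.9%. The stated figure reproduces. It counts completers, and 40 enrolled leaves room for 1 − 35/40 = 12.5% loss. The arithmetic is sound; the question is the analysis set.

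**2. Bias with no treatment effect.** Let 40% of all randomised subjects respond in both arms, and let L be the loss in an arm.

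- Case A, every lost subject a non-responder: completer rate = 0.40 / (1 − L). This is 44.4% at L = 10%, 42.1% at 5% and 41.0% at 2.5%. The false difference is +2.3 points at 10% v 5% and +3.4 points at 10% v 2.5%.
- Case B, half the losses failures and half administrative losses responding at 40%: completer rate = (0.40 − 0.40 × L/2) / (1 − L). At 10% this is 0.38/0.90 = 42.2%; at 5% it is 0.39/0.95 = 41.1%. The false difference is +1.2 points, and +1.7 points at 10% v 2.5%.
- Case C, lost subjects respond at the same 40%: no bias.

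Equal loss gives no false difference in any case. If the control arm loses more, the sign reverses (−2.3 points in case A at 5% v 10%).

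**3. Type I error.** Exact enumeration, 40 randomised per arm, two-sided 0.05:

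| Loss pattern | Pearson, case A | Pearson, case B |
|---|---|---|
| None | 5.2% | 5.2% |
| 10% v 5% | 5.7% | 5.3% |
| 10% v 2.5% | 6.2% | 5.4% |

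In case A at 10% v 5%, 4.1% of the error favours the arm with more loss, against 2.6% with no loss. Fisher's test gives 3.0% with no loss, and 3.8% (A) and 3.5% (B) at 10% v 5%. It also rises with unequal loss, but stays below 5%.

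**4. What one result can look like.** Suppose 24 v 16 responders of 40 randomised per arm, with 4 v 2 non-responders missing week 12. Completers: 24/36 v 16/38, Pearson p = 0.034. All randomised: 24/40 v 16/40, p = 0.074. This is an illustration, not a forecast.

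**5. Power after the change.** Read 73% and 40% as completer rates, so that a fraction (1 − L) of each arm responds at those rates. The mixed rule counts half of the losses as failures and leaves the other half to imputation; the strict rule counts all as failures. Exact Pearson power at 40 per arm:

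| Loss (active v control) | Completers | Mixed rule | Strict rule |
|---|---|---|---|
| 5% v 5% | 84% | 83% | 83% |
| 10% v 10% | 82% | 80% | 79% |
| 12.5% v 12.5% | 81% | 78% | 76% |
| 10% v 5% | 83% | 77% | 73% |

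The mixed column drops administrative losses, which is the available-case equivalent of imputing them within arm. A simulation with within-arm multiple imputation agreed (79.4% at equal 10% loss, 77.2% at 10% v 5%). If 73% and 40% already count losses as failures, power is 87%. In case B the mixed rule has no bias and an error of 5.1%. Covariate-based imputation and replacement of dropouts were not modelled.

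**The case against.** The set is openly defined: the reader is told who is in and who is out. Unmeasured subjects return in committed analyses, and the CONSORT counts expose the loss. On this view only the label and the ranking of analyses are at issue, and renaming the set modified ITT would cure most of it. The effect is also small: error moves by about half a point or less at 10% v 5% loss, 10% is the ceiling of the protocol's estimate, and Fisher's test stays below 5%. Finally, scoring loss by reason is a choice of estimand. It needs someone to judge reasons in a trial where section 1.25 itself says that two team members know assignments and endpoints.

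Much of this stands. The size is modest, and any classification of reasons must be blind to assignment. Renaming alone is not enough, because the headline rate would still exclude deaths from a yes/no endpoint.

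Three stronger readings are tempting and are not supported:

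- That missing data are ignored. Sections 1.24 and 1.25 commit to imputed analyses.
- That the result will favour treatment. The documents show no unequal loss, and the direction is open.
- That sections 1.28 and 1.48 rely on a property this set lacks. Section 1.28 concerns violations such as stopping the intervention, and section 1.48 concerns follow-up after withdrawal from treatment. The section 1.25 set keeps such subjects provided they are measured.

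**Conclusion.** The point holds, as a should-fix. The primary set is a week-12 completer set under an intention-to-treat label, and no rule scores death or a missed week-12 visit. The mitigation is genuine but leaves the primary denominator unchanged, and the conservative imputation is not settled.

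The size rests on assumed loss of up to 10% per arm, 40 per arm, and equal true response of 40%. At 10% v 5% the false difference is 1.2 to 2.3 points if half to all of the lost subjects are failures, and zero if loss is unrelated to outcome. Larger effects need greater imbalance, or loss above the protocol's own estimate. The replacement gap is minor: at 40 enrolled per arm it applies only above 12.5% loss.

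**What to change.** In sections 1.21.1, 1.24 and 1.25 and the Protocol Summary:

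1. Define the primary set as all randomised subjects in their assigned arm.
2. Count death before week 12 as non-response.
3. Handle other missing week-12 assessments by one rule, fixed in the SAP before analysis. Either count all as non-response, or count loss after worsening or intolerance as non-response and use the named multiple imputation for the rest. The second option needs pre-defined reasons, classified by someone blind to assignment.
4. Keep the completer analysis as a sensitivity analysis, labelled completer or modified ITT.
5. Replace the list of possible conservative imputations with one stated rule.
6. State that replaced subjects stay in the analysis.

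The cost is SAP wording and a restated power; no new data are needed. Against the completer set, power falls by about 2 to 4 points at equal 10% loss. If the active arm loses 10% and control 5%, it falls to about 73% (strict rule) or 77% (mixed rule), so the restated calculation should cover unequal loss as well.

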1.26 Statistical Power

The pivotal trial of Iloprost demonstrated that in the Iloprost arm nearly 40% had 10% improvement in 6MWD, 50% had improved FC, and 17% had both¹. From these data we calculate that 73% had either 10% improvement in 6MWD or improved functional status. Assuming metformin or the exercise arm will have similar response rate, and the placebo group will have 40% response rate, thought to be due to training effect potentially, we need 35 per group to have 80% power at 0.05 type I error rate. For the metformin and exercise combination group, an additive or synergistic effect between the two interventions will put its response rate above 73%. Thus, the combination vs. placebo comparison will have at least 80%, likely better power. From past experience coupled with the low risk, low side effect profile interventions, we estimate a dropout rate of less than 10%¹. We will enroll 40 subjects to ensure 35 completed subjects per group. The total target enrollment is 160 over 4.5 years.

1.27 Interim Monitoring Guidelines

We have not planned formal interim analyses for efficacy and therefore there are no stopping rules for efficacy for this trial. This is a Phase II trial which will be useful in supporting future studies of the intervention even if null. This project will have a DSMB who may consider whether to stop the trial or not if there is an increased risk of adverse events or toxicity.

1.28 Protocol Violations

Serious protocol violations such as discontinuation of the intervention unrelated to AEs will be carefully recorded and regularly reviewed by the Principal Investigator. Remedial changes in procedure will be recommended where feasible to reduce the incidence of

such violations. When known, the causes and circumstances of all violations will be documented for future secondary analyses and interpretation. Because all primary analyses will be intent-to-treat, it is essential that violations be kept to a minimum especially where it is possible to influence their rate of occurrence.

Study Risks and Discomforts

1.29 Activity Tracking

Digital activity tracking and text messaging do not present any obvious medical risk. Participants will be told that the text messaging system does not substitute interaction with health care providers and cannot address emergency situations. The PI will report in a timely fashion to the IRB any unanticipated problem or major study deviation.

1.30 Echocardiography

There are no risks to this ultrasound procedure aside from minor discomfort related to placement of the ultrasound probe on the chest.

1.31 Venipuncture

The protocol requires patients to have blood drawn for research purposes. The risks of drawing blood are uncommon and may include bleeding, minor infection and bruising. Commonly, having blood drawn is painful, and rarely can lead to infection at the site of the blood draw. The amount of blood drawn is small, and represents an exceedingly small percentage of the amount of the total blood volume and will not represent a significant risk to the patient.

1.32 MR Spectroscopy

A portion of the patients will have MR spectroscopy which is not associated with meaningful risk of harm to patients when patients with contraindications such as metal implants are excluded. Prior to undergoing the study procedure, enrollees will be queried about the potential presence of implanted metal by trained personnel and will not undergo this procedure if concerns arise. Claustrophobic subjects may be administered an anxiolytic if the subject has taken this medication in the past without concern. The muscle strength and function test have no known risks, but they may be lengthy, uncomfortable, or make subjects feel tired.

1.33 Metformin

This drug has been on the market for several decades and is considered first line therapy for diabetes mellitus type 2. Moreover, it has been used extensively in non-hyperglycemic patients with polycystic ovarian disease. Additional studies of the safety of metformin in heart failure have been published. The pertinent risk of metformin is development of lactic acidosis. This risk has been reported primarily in patients with abnormal renal or hepatic function, thus we have chosen to exclude these populations from the study. Additional concerns include hypoglycemia, though this is a rare risk of this drug, and gastrointestinal distress. Patients will be educated on the signs and symptoms of hypoglycemia and advised to contact study staff immediately if any arise. Several other potential side effects listed in the package insert that will be monitored at

study visits and through phone conversation if need arises. We will monitor patients at baseline, week 1, week 3, week 6, week 9, week 12, week 15, and week 17 through either a visit or phone conversation. At these points, side effects that limit dose adjustment will be assessed. If patients report significant gastrointestinal effects, metformin will not be increased as would otherwise occur in the protocol. If symptoms persist further, the dose will be dropped by 500 mg daily to the highest tolerated dose.

The most common adverse reactions experienced are:

- >10% of patients: diarrhea (instant release tablet: 12% to 53%; extended release tablet: 10% to 17%), nausea/vomiting (instant release tablet: 7% to 26%; extended release tablet: 7% to 9%), flatulence (12%), Weakness (9%)
- 1% to 10%: chest discomfort, flushing, palpitation, headache (6%), chills, dizziness, lightheadedness, rash, hypoglycemia, Indigestion (7%), abdominal discomfort (6%), abdominal distention, abnormal stools, constipation, dyspepsia/heartburn, taste disorder, myalgia, dyspnea, upper respiratory tract infection, decreased vitamin B₁₂ levels (7%), increased diaphoresis, flu-like syndrome, nail disorder
- <1% (Limited to important or life-threatening): lactic acidosis, leukocytoclastic vasculitis, megaloblastic anemia, pneumonitis
- Contraindications to the use of metformin are: hypersensitivity to metformin or any component of the formulation; renal disease or renal dysfunction (serum creatinine ≥ 1.5 mg/dL in males or ≥ 1.4 mg/dL in females) or abnormal creatinine clearance from any cause, including shock, acute myocardial infarction, or septicemia; acute or chronic metabolic acidosis with or without coma (including diabetic ketoacidosis)

1.33.1 *Boxed Warning*

A boxed warning has been issued for metformin related to the risk of developing lactic acidosis. The risk is increased in patients with acute congestive heart failure, dehydration, excessive alcohol intake, hepatic or renal impairment, or sepsis. Conditions that increase the risk of lactic acidosis on metformin treatment are all exclusion criteria for this study. Based on our pilot trial with no lactic acidosis in enrollees thus far, we do not anticipate this to be a significant complication. If clinically significant lactic acidosis is diagnosed for clinical indications, the DSMB and IRB will be notified as per protocol.

1.33.2 *Iodinated Contrast*

Metformin therapy will be discontinued prior to or at the time of intravascular administration of iodinated contrast media (potential for acute alteration in renal function) should a subject require contrast during the course of this study. Metformin will be withheld for 48 hours after the radiologic study and restarted only after renal function has been confirmed as normal. Patients will be encouraged to delay any elective radiologic studies requiring iodinated contrast until the conclusion of the study.

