"Interventions Against Insulin Resistance in Pulmonary Arterial Hypertension"

PI: Drs. [name], [name], and [name]

Vanderbilt University Medical Center

NCT #: NCT03617458

Most recent IRB Approval Date: 4/12/2024

Interventions Against Insulin Resistance in Pulmonary Arterial Hypertension

Date: December 26, 2021

Version: 6.1

Principal Investigator: [name]
[name]
[name]
[name]

[contact]

[contact]

Email: [contact]

Confidential Information

Revision History:

Version 1.0	1/12/2018
Version 1.1	5/30/2018
Version 2.1	7/25/2018 – Sub study revisions
Version 3	2/22/2019 – 1. Change of PFT exclusion criteria, Change of visit window for week 12, medication clarification
Version 3.1	May 31, 2019 - Addition of muscle fatigue language and change of eGFR exclusion criteria. Addition of econsent use.
Version 3.2	10/29/2019 Clarification of inclusion/exclusion criteria and addition of Redcap Clinical Data Pull verbiage.
Version 3.3	Fix version error (V3.2 footer still said “version 2.”)
Version 4	Inclusion/Exclusion criteria changes
Version 5	Addition of language to include ability to contact patients via EMR and by email
Version 6	eGFR exclusion criteria change & Scleroderma inclusion criteria addition
Version 6.1	12.26.2021 - Amend “Scleroderma” inclusion/exclusion criteria to read, “connective tissue disease – associated PAH” to broaden inclusion

Protocol Summary

OBJECTIVES:

The primary objective of this study is to determine the impact of two interventions against insulin resistance on the composite endpoint of 10% improvement in baseline six minute walk distance or improvement in WHO functional class.

Secondary objectives include:

- To assess the effect of an mHealth intervention or no intervention and/or metformin or placebo on body weight at week 12.
- To assess the effect of a mHealth intervention or no intervention and/or metformin or placebo on BMI at week 12.
- To assess the effect of a mHealth intervention or no intervention and/or metformin or placebo on absolute 6MWD at week 12.
- To assess the effect of a mHealth intervention or no intervention and/or metformin or placebo on Borg Dyspnea Score at week 12.
- To assess the effect of a mHealth intervention or no intervention and/or metformin or placebo on emPHasis-10 quality of life survey score at week 12.

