1.8 Recruitment of Study Sample

Patients will be recruited from the Center for Pulmonary Vascular Disease (CPVD) at Vanderbilt University Medical Center (Nashville, TN), the Pulmonary Hypertension Clinic at Mayo Clinic (Rochester, MN), and the Pulmonary Hypertension Program at Cleveland Clinic (Cleveland, OH). Study sites may be contacting, communicating, and recruiting participants by, 1) telephone, 2) email using their assigned institution email address or, 3) through a secure patient portal and associated electronic medical record.

Potentially eligible subjects will be pre-screened and informed about that study to determine if they have an interest in enrolling. After the initial pre-screening, the subject will provide in-person informed consent or e-consent before any study procedures are performed.

1.9 ResearchMatch.org will also be utilized as a recruitment tool for this protocol. ResearchMatch.org is a national electronic, web-based recruitment tool that was created through the Clinical & Translational Science Awards Consortium in 2009 and is maintained at Vanderbilt University as an IRB-approved data repository (see IRB #090207).Inclusion/Exclusion Criteria

Inclusion criteria:

- Adults aged 18 or older.
- Diagnosed with idiopathic, heritable, connective tissue disease – associated PAH, or drug- or toxin-associated pulmonary arterial hypertension (PAH) according to World Health Organization consensus recommendations.
- Repaired simple congenital heart disease or unrepaired ASD
- Stable PAH-specific medication regimen for three months prior to enrollment. Subjects with only a single diuretic adjustment in the prior three months will be included. Adjustments in IV prostacyclin for side effect management are allowed.
- Subjects must own a Bluetooth capable modern smartphone capable of receiving and sending text messages and an active data plan.
- FEV1 > or = 60% predicted and no more than mild abnormalities on lung imaging
- WHO Functional Class I-III
- Ambulatory

Exclusion criteria:

- Prohibited from normal activity due to wheelchair bound status, bed bound status, reliance on a cane/walker, activity-limiting angina, activity-limiting osteoarthritis, or other condition that limits activity.
- Pregnancy
- Diagnosis of PAH etiology other than idiopathic, heritable, connective tissue disease – associated PAH, or associated with drugs or toxins
- Drug and toxin associated PAH patients with active drug use
- WHO Functional class IV heart failure

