- FEV1< 60% predicted with more than mild abnormalities on lung imaging
- Requirement of > 1 diuretic adjustment in the prior 30 days
- Preferred form of activity is not measured by an activity tracker (swimming, ice skating, stair master, or activities on wheels such as bicycling or rollerblading)
- Type I diabetes mellitus
- Prior diagnosis of cirrhosis
- Untreated hypo- or hyper-thyroidism
- eGFR by MDRD <40mL/min

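### No criterion keeps current metformin users out of a metformin trial; secondly, the safety text claims lactic-acidosis exclusions that the eligibility lists do not contain

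*Combined protocol and SAP*

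**What the plan says.** **Eligibility.** The exclusion criteria appear in the Protocol Summary and again under Inclusion/Exclusion Criteria (section 1.9), with the same items. The only diabetes item is type I. The only hepatic item is "Prior diagnosis of cirrhosis". The renal item is "eGFR by MDRD <40mL/min". One item excludes active drug use, but only in drug- or toxin-associated PAH, and it does not name alcohol. Neither list mentions metformin. The requirement for a stable regimen covers PAH-specific drugs.

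**Study drug.** Section 1.16 titrates 500 mg tablets over 15 days to two tablets twice daily and bases the schedule on tolerability in the pilot. Section 1.6 gives the pilot maximum as 1 g twice daily. Section 1.33 describes metformin as the usual first choice in type 2 diabetes. Section 1.19 says that a participant's existing medication is left as it is.

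**Safety text.** Section 1.33 says that lactic acidosis is reported mainly with "abnormal renal or hepatic function, thus we have chosen to exclude these populations from the study". Section 1.33.1 states: "The risk is increased in patients with acute congestive heart failure, dehydration, excessive alcohol intake, hepatic or renal impairment, or sepsis". Its next sentence reads: "Conditions that increase the risk of lactic acidosis on metformin treatment are all exclusion criteria for this study". Between the two, a list of general contraindications to the drug includes "renal disease or renal dysfunction (serum creatinine" with sex-specific cut-offs of 1.5 mg/dL (men) and 1.4 mg/dL (women).

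**The concern.** A trial of a widely used drug normally says what happens to people who already take it. This one does not, although its population can include patients with type 2 diabetes, for whom the protocol itself regards metformin as standard. Two things are at stake. The first is exposure: a user assigned to active tablets takes two sources of metformin. The second is what the comparison means: a user contributes information on adding study metformin to existing metformin, not on metformin against none.

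The secondary matter is an assurance that the criteria do not deliver. Under section 1.19.1 an investigator confirms the listed criteria before randomisation. A patient whom the safety text describes as kept out, such as one with heavy alcohol intake or non-cirrhotic hepatic impairment, can therefore satisfy the list. The entry check carries weight because the comprehensive panel is scheduled only at screening and week 12 (Table 2 and section 1.22.8), and section 1.46.5 limits other laboratory tests to clinical need.

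**Working it through.** **1. Can a current user be randomised?** Each provision that might prevent it was checked.

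- Diabetes item: type I only, so type 2 is admissible.
- Concomitant medication: no prohibited-drug rule names metformin.
- Washout: none is described before entry. The wash-out column in Table 2 follows the treatment period.
- Background regimen: unchanged (section 1.19).
- Medication review: done at screening (section 1.19.1), but tied to no criterion on metformin.

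A user who meets the other criteria can therefore be randomised. Two of the four arms receive metformin, 2 × 40 = 80 of the planned 160, so the chance of assignment to active tablets is 80/160 = 50%.

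**2. Dose.** The inputs are the 500 mg tablet and the steps in section 1.16, and the pilot maximum of 1 g × 2 = 2,000 mg/day in section 1.6. With study dose S, the total exceeds the pilot maximum when the open-label dose is above 2,000 − S.

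| Step | Study dose S (mg/day) | Open-label dose that takes the total above 2,000 mg/day |
|---|---|---|
| Days 1–5 | 1 × 500 = 500 | more than 1,500 |
| Days 6–10 | 2 × 500 = 1,000 | more than 1,000 |
| Days 11–15 | 3 × 500 = 1,500 | more than 500 |
| Day 16 on | 4 × 500 = 2,000 | any |

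The documents give no open-label doses. Assuming 0.5 to 2 g/day, the total at full study dose is 2.5 to 4 g/day, or 2.5/2 = 1.25 to 4/2 = 2 times the pilot maximum. A user held at 1 g/day of study drug with 0.5 to 1 g/day open-label takes 1.5 to 2 g/day, which does not exceed it.

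**3. Effect on the contrast.** The primary endpoint is improvement over the screening measurement. A user's screening walk and functional class already include any benefit from existing metformin. On active tablets such a patient can show only the effect of added dose; on placebo, the comparator is not metformin-free. Let m be the share of users and b the fraction of the planned benefit that added metformin still gives them, and assume that users on placebo respond at the planned 40%. The planned difference of 0.73 − 0.40 = 0.33 then becomes 0.33 × [1 − m(1 − b)]. The documents give neither m nor b, so no numerical loss is claimed.

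**4. Safety text against the lists.**

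| Condition named in section 1.33.1 | What the lists contain |
|---|---|
| Excessive alcohol intake | No item |
| Hepatic impairment | Prior cirrhosis only. The item that begins "Diagnosis of PAH etiology other than idiopathic, heritable" removes PAH attributed to liver disease, but not coexisting hepatic impairment without cirrhosis |
| Renal impairment | eGFR by MDRD below 40 mL/min |

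The word all in section 1.33.1 is therefore not true of the lists. The section 1.33 sentence on abnormal renal or hepatic function is broader than the two items that implement it. Acute heart failure, dehydration and sepsis are largely transient states and are not pressed here, though a reworded sentence should not claim them either.

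**The case against.** The best defence is practical. Current drugs are reviewed at screening, so a site would probably notice metformin and hesitate. The sentence in section 1.19 describes visits and is not a concomitant-medication policy. Calls through week 17, holding or lowering the dose for persistent gastrointestinal effects (section 1.33), investigator withdrawal (section 1.48) and the DSMB (section 1.43) all limit harm. Nothing shows that a user has been enrolled. All of this stands, and it limits the severity. It does not close the gap, because no written rule tells a site to exclude a user it has noticed.

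On the secondary point, investigators apply the lists and not section 1.33, the lists do contain renal and hepatic items, and rewording alone would make the text true. That stands too, which is why it is secondary.

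A reader might also infer that the creatinine cut-offs and the eGFR limit are competing eligibility rules, or that the eGFR limit is wrong. The documents do not support this. The creatinine figures belong to a general list of drug contraindications. The eGFR limit is the trial's own rule and was deliberately revised; the Revision History entry for version 6 reads "eGFR exclusion criteria change & Scleroderma inclusion criteria addition".

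**Conclusion.** The point holds, and an amendment is warranted. The main gap is that current metformin users are eligible. Such a user has a 50% chance of receiving study metformin in addition to their own. At the full 2 g/day any open-label dose exceeds the pilot experience; at lower tolerated study doses it may not. The 1.25- to 2-fold range rests on an assumed open-label dose of 0.5 to 2 g/day.

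Two stronger readings should be resisted. One is that the trial is underpowered because of users: the number of users and their residual benefit are not given, so the dilution is real in principle but cannot be sized. The other is that every user would exceed the pilot maximum, which the titration and dose-lowering rules contradict.

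The mismatch between safety text and lists is a smaller, certain error of wording or coverage. It rests on direct comparison of the sections and on no calculation.

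**What to change.** 1. Add current metformin use to the exclusion criteria in both the Protocol Summary and section 1.9. Any washout interval is for the investigators to set. Recording use and adjusting for it in the analysis would not prevent combined dosing.
2. Make the safety text and the lists agree. Either add excessive alcohol intake and clinically significant hepatic impairment to both lists, the latter judged on the comprehensive panel already drawn at screening with a threshold chosen by the investigators, or reword the sentences in sections 1.33 and 1.33.1 to name only conditions actually excluded.
3. Leave the general contraindication list as it is, and add one sentence stating that the trial's renal rule is exclusion at eGFR by MDRD below 40 mL/min.

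The cost is an amendment of up to three list lines in two places and a few sentences, with no new test. Item 1 loses some otherwise eligible patients with type 2 diabetes, against a target of 160 over 4.5 years. The list additions in item 2, if chosen, would exclude some further patients.
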